#### 4.2.1.1.2 Presentation

Duration of exposure to IP in days is summarised by descriptive statistics and by frequency. Dose intensities are summarised by descriptive statistics and by the categories <75, 75-125, and >125. Exposure to IP, i.e., total amount of study drug received, are listed for all participants.

Exposure swimmer plot(s) are produced, with a line presented for each participant to display relevant exposure and disposition details.

Dosing deviations for IP are summarised with reasons for deviations for the following categories: delays and interruptions. The frequency counts and percentage of the number of participants with delays and/or interruptions and total count per participant are summarised. The frequency counts and percentage of the number of participants with dosing delays and total count dose delays per participant are summarised.

#### 4.2.1.2 Adverse Events

MedDRA (using the latest or current version) are used to code the AEs. AEs are graded according to the National Cancer Institute Common Terminology Criteria for AEs (NCI CTCAE) (using the CTCAE version referenced in the CSP).

Treatment emergent AEs (TEAEs) are all AEs which onset or worsen in severity following the first administration of IP within the duration of the treatment period, up to and including 97 days [90 days +/- 7 days] after the last dose of IP as per the study safety follow up period

but prior to subsequent cancer therapy. Worsening in severity is determined by comparison with the pre-treatment CTCAE grade of the AE recorded closest to the start of dosing.

For rules on missing or partial dates, see Section [3.3.6](#). AEs with a missing start time (or where time is not collected) which occur on the same day as first IP administration are reported as treatment emergent SAEs.

When assigning AEs to the relevant phase of the study the following rules apply and any deviations must be agreed by the study team:

- Pre-treatment phase: All AEs with a start date after signing the informed consent form (ICF), prior to the first administration of IP that do not subsequently go on to worsen during the treatment emergent phase.
- Treatment emergent phase: All AEs (starting or worsening) on or after the first dose of study intervention and within 97 days [90 days +/- 7 days] after the last dose of study IP or up to the day prior to start of subsequent therapy, whichever comes first.

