3 OBJECTIVES AND ENDPOINTS

Table 4 Objectives and Endpoints

Please see the study-specific objectives and endpoints for each Substudy within the respective Substudy section. The following objectives are applicable for all Substudies.

Type	Objectives	Endpoints	
Primary			
Safety	To assess safety and tolerability, characterise DLTs (in dose escalation parts only) and determine the MTD or RP2D of AZD8853 in participants with selected advanced/metastatic solid tumours in each Substudy	 Incidence of AEs and SAEs Incidence of DLTs in dose escalation parts only Incidence of clinically significant changes from baseline in clinical laboratory parameters, vital signs, and ECG results Incidence of AEs leading to discontinuation of AZD8853 	
	Secondary		
Efficacy	To determine the preliminary anti-tumour activity of AZD8853 in participants with selected advanced/metastatic solid tumours in each Substudy To assess the efficacy of AZD8853 using longitudinal blood samples in participants with selected advanced/metastatic solid tumours in each Substudy	According to RECIST v1.1 ORR, DCR at Week 15, DoR, and PFS Change in target lesion tumour size from baseline OS Change in ctDNA from baseline levels between baseline and post-treatment timepoints	
PK	To determine the PK of AZD8853 in serum when administered in participants with selected advanced/metastatic solid tumours in each Substudy	PK parameters to be evaluated include but not limited to Cmax and AUC	
Immunogenicity	To assess the immunogenicity of AZD8853 in participants with selected advanced/metastatic solid tumours in each Substudy	Number and percentage of participants who develop detectable ADAs against AZD8853 in serum samples	

Abbreviations: ADA = antidrug antibodies; AE = adverse event; AUC = area under the concentration time curve; Cmax = maximum observed concentration; ctDNA = circulating tumour deoxyribonucleic acid; DCR = disease control rate; DLT = dose limiting toxicity; DoR = duration of response; ECG = electrocardiogram; MTD = maximum tolerated dose; ORR = objective response rate; OS = overall survival; PD = pharmacodynamic(s); PFS = progression free survival; PK = pharmacokinetic(s); RECIST = response evaluation criteria in solid tumours; RP2D = recommended Phase 2 dose; SAE = serious adverse event.

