8.3.2 Follow-up of AEs and SAEs

Any AEs that are unresolved at the participant's last assessment in the study are followed up by the Investigator for as long as medically indicated, but without further recording in the eCRF. These AEs must still be reported to the Sponsor and records must be kept with the participant's record. AstraZeneca retains the right to request additional information for any participant with ongoing AE(s)/SAE(s) at the end of the study, if judged necessary.

Adverse event variables

The following variables will be collected for each AE:

- AE (verbatim)
- The date and time when the AE started and stopped
- CTCAE grade/changes in CTCAE grade
- Whether the AE is serious or not
- Investigator causality rating against the study intervention(s) (yes or no)
- Action taken with regard to study intervention(s)
- AE caused participant's withdrawal from study (yes or no)
- Outcome, including administration of any treatment

In addition, the following variables will be collected for SAEs:

- Date AE met criteria for SAE
- Date Investigator became aware of SAE
- AE is serious due to
- Date of hospitalisation
- Date of discharge
- Probable cause of death
- Date of death
- Autopsy performed
- Causality assessment in relation to study procedure(s)
- Causality assessment to other medication

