Participants from terminated sites will have the opportunity to be transferred to another site to continue the study.

A 10 Publication Policy

- The results of this study may be published or presented at scientific meetings. If this is foreseen, the Investigator agrees to submit all manuscripts or abstracts to the Sponsor before submission. This allows the Sponsor to protect proprietary information and to provide comments.
- The Sponsor will comply with the requirements for publication of study results. In accordance with standard editorial and ethical practice, the Sponsor will generally support publication of multicentre studies only in their entirety and not as individual site data. In this case, a coordinating Investigator will be designated by mutual agreement.
- Authorship will be determined by mutual agreement and in line with International Committee of Medical Journal Editors authorship requirements.

Appendix B Adverse Events: Definitions and Procedures for Recording, Evaluating, Follow-up, and Reporting

B 1 Definition of Adverse Events

An AE is the development of any untoward medical occurrence in a patient or clinical study participant administered a medicinal product and which does not necessarily have a causal relationship with this treatment. An AE can therefore be any unfavourable and unintended sign (eg, an abnormal laboratory finding), symptom (for example nausea, chest pain), or disease temporally associated with the use of a medicinal product, whether or not considered related to the medicinal product.

The term AE is used to include both serious and non-serious AEs and can include a deterioration of a pre-existing medical occurrence. An AE may occur at any time, including run-in or washout periods, even if no study treatment has been administered.

B 2 Definitions of Serious Adverse Event

A serious adverse event is an AE occurring during any study period (ie, run-in, treatment, washout, follow-up), that fulfils one or more of the following criteria:

- Results in death
- Is immediately life-threatening
- Requires in-participant hospitalisation or prolongation of existing hospitalisation
- Results in persistent or significant disability or incapacity
- Is a congenital anomaly or birth defect
- Is an important medical event that may jeopardise the participant or may require medical treatment to prevent one of the outcomes listed above.

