**Table 3: Core Endpoint analysis**

Statistical category	Endpoint	Population	Population level summary (analysis)	Details in section
Objective 1: To assess safety and tolerability, characterize DLTs (in dose escalation parts only) and determine the MTD or RP2D of AZD8853 in participants with selected advanced/metastatic solid tumours				
Primary	AEs, SAEs, clinically significant changes from baseline in clinical laboratory parameters, vital signs, and ECG results, Incidence of AEs leading to discontinuation of AZD8853.	Safety analysis set	Percentage of participants with AEs, SAEs, clinically significant changes from baseline in clinical laboratory parameters, vital signs, and ECG results. Percentages of participants with AE leading to discontinuation	4.2.1
Objective 2: To determine the preliminary anti-tumour activity of AZD8853 in participants with selected advanced/metastatic solid tumours				

Statistical category	Endpoint	Population	Population level summary (analysis)	Details in section
Secondary	ORR according to RECIST v 1.1	Response evaluable set	Rate and 90% CI (2-sided CI)	4.2.2
Secondary	DCR at Week 15 according to RECIST v 1.1	Response evaluable set	Rate and 90% CI (2-sided CI) for each cohort at 15 weeks.	4.2.4
Secondary	DoR according to RECIST v 1.1	Subset of response evaluable set: participants with confirmed objective response	Kaplan-Meier plots and median DoR time estimated using Kaplan Meier method.	4.2.5
Secondary	PFS	Safety analysis set	Kaplan-Meier plots and median PFS time estimated using Kaplan Meier method.	4.2.6
Secondary	Change in target lesion tumour size	Response evaluable set	Percentage change in tumour size from baseline, at each timepoint is summarized by mean change and St Dev  Percentage change from baseline for each participant is produced over time in a spider plot.  Waterfall plots of percentage change from baseline and best percentage change from baseline is produced.	4.2.7
Secondary	OS	Safety analysis set	Kaplan-Meier plots and median OS time estimated using Kaplan Meier method.	4.2.8
Objective 3: To assess the efficacy of AZD8853 using longitudinal blood samples in participants with selected advanced/metastatic solid tumours				

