### **SAEs**

An SAE is an AE occurring during any study period that fulfils one or more of the following criteria:

- Results in death
- Is immediately life-threatening
- Requires inpatient hospitalization or prolongation of existing hospitalization
- Results in persistent or significant disability/incapacity
- Is a congenital anomaly/birth defect in offspring of the participant
- Is an important medical event that may jeopardize the participant or may require medical treatment to prevent one of the outcomes listed above.

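### The SAP's rule for Day-1 adverse events with no start time says SAEs where it almost certainly means AEs; programmed as written, it would assign seriousness from a missing time

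*SAP*

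**What the plan says.** SAP section 4.2.1.2 defines treatment-emergent adverse events, refers to section 3.3.6 for missing and partial dates, and then gives one rule for missing times. The rule covers "AEs with a missing start time (or where time is not collected") and continues: "which occur on the same day as first IP administration are reported as treatment emergent SAEs". The rule starts from all AEs and nothing in it limits it to serious ones.

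The SAE subsection that follows in the SAP says "An SAE is an AE occurring during any study period that fulfils one or more of the following criteria", and lists death, threat to life, hospitalisation, disability, congenital anomaly and important medical event. Protocol Appendix B 2 opens its definition in the same way ("A serious adverse event is an AE occurring during any study period") and gives equivalent criteria.

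Protocol section 8.3.2 lists the variables collected for each AE. They include "Whether the AE is serious or not" and "The date and time when the AE started and stopped".

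Protocol section 3 has "Incidence of AEs and SAEs" among the primary endpoints. SAP Table 3 summarises the primary safety endpoint as "Percentage of participants with AEs, SAEs, clinically significant changes from baseline in clinical laboratory parameters, vital signs, and ECG results".

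**The concern.** A rule for a missing clock time should settle one question: did the event start before or after the first infusion? This sentence also answers a second question, whether the event was serious, and answers it yes for every event that it covers. A missing time carries no information about seriousness.

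The sentence is an operative derivation rule that feeds a primary endpoint. SAEs have their own tables in SAP section 4.2.1.2.1, and section 3.1.1 presents Part A by dose level, where denominators are small. Events on the first-dose day are foreseeable: protocol section 8.3.6, in partly redacted text, describes reactions seen commonly during or shortly after first exposure to infused antibodies. A literal program would put any of these that lacked a time into the SAE tables.

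**Working it through.** The plan gives no figure to reproduce here. The check is a comparison of texts, followed by simple fractions to show scale.

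**1. The rule against the definitions.**

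| Source | What decides that an event is an SAE |
|---|---|
| SAP 4.2.1.2, missing-time rule | First-dose date and no start time |
| SAP 4.2.1.2, SAE subsection | At least one seriousness criterion |
| Protocol Appendix B 2 | At least one seriousness criterion |
| Protocol 8.3.2 | Serious yes/no recorded for each AE |

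The first row conflicts with the other three. No other part of the SAP corrects it.

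**2. What the rule was for.** The sentences around it concern treatment emergence: the TEAE definition, the reference to the missing-date rules and the assignment of events to study phases. SAP section 3.3.6 says that imputed dates generally serve to decide treatment emergence. Seriousness has no role in any of this, which points to SAEs having been written for AEs.

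**3. Which events are exposed.**
- Day-1 AEs whose time is missing or was not captured. Start time is a listed variable in protocol 8.3.2, which limits this group.
- Possibly AEs with incomplete start dates. SAP 3.3.6 imputes the first-dose date when the day is missing and the month matches that of first dose, or when day and month are missing and the year matches. It does the same when the whole date is missing, unless the end date suggests an earlier start. I assume that such records usually lack a time too. The rule could then reach events that did not begin on Day 1.

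**4. The alternative reading.** Suppose a programmer takes the rule to cover only events already recorded as serious. Then non-serious Day-1 AEs without a time have no explicit rule. The TEAE definition asks for onset or worsening following first administration, which cannot be verified without a time. The phase-assignment rule speaks of events on or after the first dose. That could be read by date and would bring them in, but it does not say what to do when the time is missing.

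**5. Scale, as illustration only.** The documents give neither the number of Day-1 AEs nor the share without a time. Take one participant whose only counted SAE is a non-serious event caught by the rule. The SAE percentage then rises by 100 × 1/n points:

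| Group | n | Increase (points) |
|---|---|---|
| Part A, smallest cohort | 3 | 100 × 1/3 = 33 |
| Part A, upper end of initial enrolment | 5 | 100 × 1/5 = 20 |
| Part A, largest cohort | 9 | 100 × 1/9 = 11 |
| Part B, one tumour type at one dose | 10 | 100 × 1/10 = 10 |
| Part B, one dose level | 20 | 100 × 1/20 = 5 |
| Part C, one expansion | 40 | 100 × 1/40 = 2.5 |

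The cohort sizes come from protocol sections 10.4.1 and 10.6.6.1.3. A participant who already has a genuine SAE adds nothing to the percentage. With the wording corrected, every increase is zero and the events stay in the TEAE tables.

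**The case against.** The strongest reply is that this is one stray letter and not an analysis decision. The context is treatment emergence throughout, the SAE definition follows at once, and the investigator's seriousness entry is in the database. A programmer would have to override that entry to produce the error, and most would notice. Start times are meant to be collected, so few events should qualify. The large percentages belong to the smallest cohorts; SAP section 4.2 also plans presentations that pool parts for the same dose and disease, where one event weighs less.

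All of that stands, and it is why the point is minor. It does not remove the contradiction, because a derivation rule should not depend on the programmer to recognise that it is misworded.

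A reader might go further and infer that the reported SAE rate will be inflated, or that dose decisions are at risk. The documents support neither. The error arises only under literal programming, and its frequency is unknown. Escalation and the MTD rest on DLTs (protocol 10.6.6.1.3; SAP 4.2.1.8), which for reporting are those documented by the Safety Review Committee. SAE incidence is one of several primary safety measures, alongside AEs, DLTs, discontinuations, and laboratory, vital-sign and ECG changes. Nor do the documents say what share of first-infusion events is non-serious, so no argument should rest on that share.

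**Conclusion.** The sentence is wrong as written and very probably a drafting slip. It contradicts the SAE definitions in both documents and feeds a primary endpoint, so it should be corrected, as a minor point. The harm is conditional on the rule being programmed literally over the collected seriousness item. Its size cannot be estimated from the documents; the range of 2.5 to 33 points per affected participant only shows how one misclassified event would weigh in groups of 40 down to 3. That range assumes the participant has no other SAE. That incomplete dates are also caught rests on the assumption that those records have no time. DLT counts, dose escalation and the MTD are not affected.

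**What to change.** In SAP section 4.2.1.2, replace *treatment emergent SAEs* in the missing-time sentence with *treatment emergent AEs (TEAEs)*. Add one sentence stating that seriousness is taken only from the investigator's eCRF seriousness item (protocol section 8.3.2) and is never derived from dates or times. The replacement also gives non-serious Day-1 events without a time an explicit treatment-emergence rule.

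The cost is a changed term and one added sentence. No data collection or intended analysis changes. If outputs have already been programmed, check that the SAE flag follows the eCRF item.

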### **SAEs**

An SAE is an AE occurring during any study period that fulfils one or more of the following criteria:

- Results in death
- Is immediately life-threatening
- Requires inpatient hospitalization or prolongation of existing hospitalization
- Results in persistent or significant disability/incapacity
- Is a congenital anomaly/birth defect in offspring of the participant
- Is an important medical event that may jeopardize the participant or may require medical treatment to prevent one of the outcomes listed above.

### **AEs of special interest**

An Adverse Event of Special Interest (AESI) is one of scientific and medical interest specific to understanding of the study intervention and may require close monitoring and rapid communication by the investigator to the sponsor. AESIs include but are not limited to:

- CCI [REDACTED]
- CCI [REDACTED]

- CCI [REDACTED]
- CCI [REDACTED]
- CCI [REDACTED]
- CCI [REDACTED]

Other AEs which are AESIs with AZD8853 include, but are not limited to:

- CCI [REDACTED] )
- CCI [REDACTED]
- CCI [REDACTED]
- CCI [REDACTED]

More information regarding AESIs can be found in the CSP section 8.3.6. Other categories may be added, or existing terms may be modified as necessary. An AstraZeneca medically qualified expert after consultation with the Global Patient Safety Physician has reviewed the AEs of interest and identified which higher-level terms and which preferred terms contribute to each AESI. Further reviews may take place prior to DBL to ensure any further terms not already included are captured within the categories. Preferred terms used to identify AESI is listed before DBL.

### **Other Significant Adverse Events (OAE)**

During the evaluation of the AE data, an AstraZeneca medically qualified expert reviews the list of AEs that were not reported as SAEs and AEs leading to discontinuation of IP. Based on the expert's judgement, AEs of clinical importance may, after consultation with the Global Safety Physician, be considered OAEs and reported as such in the CSR. A similar review of laboratory values, vital signs, ECGs, and other safety assessments are performed for identification of OAEs. This review takes place prior to DBL, and any AEs identified are fully documented in meeting minutes. Further review following DBL may result in ad-hoc OAEs being identified, in this case, the OAEs and resulting summaries are fully documented in the CSR.

Examples of these are marked haematological and other laboratory abnormalities, and certain events that lead to intervention (other than those already classified as serious), dose reduction or significant additional treatment.

#### 4.2.1.2.1 Presentation

All TEAEs are summarised and listed. AEs which are not treatment emergent are listed for the safety analysis set.

TEAEs are counted once for each participant for calculating percentages of participants experiencing TEAE. In addition, if the same TEAE occurs multiple times within a participant, the highest severity, and level of relationship observed are reported. For tables by MedDRA SOC and MedDRA PT, participants with multiple TEAEs are counted once for each SOC/PT.

An overall summary table of the number of participants experiencing each category of AEs is produced. The number of participants experiencing TEAEs by MedDRA SOC and PT are summarised and the severity, and relationship to study drug are summarised. Further splits by CTCAE grade, causal relationship to IP and AEs with Grade 3-5 are also summarised.

Separate tables present DLTs (applicable for Substudy 1 Part A only), AEs leading to discontinuation, SAEs, IP-related AEs, and other significant adverse events.

Details of any deaths are summarised and listed for all participants. SAEs leading to death are also summarised.

#### SAEs

SAEs are summarised as described above for the TEAEs.

#### AEs of special interest

Grouped summary tables of certain MedDRA preferred terms are produced and may also show the individual preferred terms which constitute each AESI grouping. Groupings are based on preferred terms provided by the medical team prior to DBL, and a listing of the preferred terms in each grouping is provided.

Summaries of the above-mentioned grouped AE categories include number and percentage (%) of participants who have:

- At least one AESI presented by event outcome
- At least one AESI causally related to IP
- At least one AESI leading to discontinuation of IP.

A summary of total duration (days) of AESI is provided for events which have an end date, and this may be supported by summaries of ongoing AESIs at death and, separately, at DCO.

#### 4.2.1.3 Clinical Laboratory, Blood Sample

##### 4.2.1.3.1 Definitions and Derivations

Laboratory tests are grouped according to chemistry, haematology, and coagulation. Laboratory parameters are assessed at baseline as well as throughout the study.

For chemistry, haematology, and coagulant parameters, laboratory abnormalities with toxicity grades according to the NCI CTCAE version 5.0 are derived.

Change from baseline in haematology, clinical chemistry and coagulation endpoints are calculated for each post-dose visit. CTC grade is calculated at each visit. Maximum post-baseline CTC are also calculated. Absolute values are compared to the local laboratory reference range and classified as low (below range), normal (within range or on limits of range) and high (above range). All values classified as high or low are flagged on the listings.

